End stage renal disease leads to accumulation of different sized molecules and toxins. Dialysis patients routinely undergo haemodialysis (HD) treatment three times per week. Standard dialysis treatment utilizes traditional dialysis membranes which provide size specific clearance lead to accumulation of larger molecules {such as Fibroblast Growth Factor-23 (FGF-23) molecular weight: 32 KiloDaltons (KDa)}. Accumulation of FGF-23 is thought to be associated with increased cardiovascular events and overall mortality in dialysis patients. Newer dialysis membranes so called medium cut-off (MCO) membrane (e.g Theranova by Baxter Healthcare) can potentially clear relatively bigger sized molecules due to bigger pore size No data is available regarding clearance of FGF-23 on MCO membranes. The aim of this study is to investigate the new membranes can remove FGF 23.

This study will include adult patients with renal failure who are on long term HD at Salford HD Unit and Bolton HD Unit which is a satellite unit of Northern Care Alliance NHS Foundation Trust. During this study, patients will be randomized to 1 week monitored HD treatment with MCO membrane followed by 1 week monitored conventional HD or to receive 1 week monitored conventional HD followed by 1 week monitored MCO membrane treatment. Both options will include a 3-week interval between monitored sessions during which the patients will receive conventional HD. Blood samples will be collected before and after dialysis during monitored treatment week. Blood samples will be tested for FGF-23 levels but also for calcium, phosphate levels, Vitamin D and PTH levels which are known to affect FGF-23 levels. In addition to blood sample, dialysate generated during the monitored dialysis session will be collected and analyzed for solute levels including FGF-23 levels.

Generated data will be analysed to compare clearance of FGF-23 on conventional dialysis membranes versus clearance on MCO membrane and rate of re-accumulation of FGF-23 between dialysis sessions. If the new membrane is effective in removing FGF 23 further studies should explore the impact of the new membranes on cardiovascular profiles and cardiovascular outcomes

2 Study Team Roles and Responsibilities

2.3 Funding

Northern Care Alliance NHS Foundation Trust

Kidneys for life: "Proteomic analysis of molecules exchanged using new medium cut-off dialysis membrane. "£10000 to be paid six monthly in arrears on production of expenditure report. All grants must be claimed by 31 December 2019 unless permission has been sought to extend this date. Baxter: Investigator initiated research grant £10,600 upon receipt of executed Agreement and proof of registration on www.clinicaltrials.gov

Despite technological advances in the field of renal replacement therapy, mortality in haemodialysis (HD) patients remains high, comparable with cancer patients. The leading cause of death is cardiovascular disease. It is postulated that specific factors related to end stage renal disease play a detrimental role in increasing cardiac risk. One factor that has been identified is FGF-23, a molecule that increases with progressive renal dysfunction and causes uraemic cardiomyopathy in experimental models. FGF 23 levels remain high in HD patients receiving current standard dialysis treatment that removes largely small molecules. The new Baxter medium cut-off membrane (MCO, Theranova, Baxter Healthcare) has a higher molecular weight cut-off than conventional membranes that facilitates removal of larger i.e. medium-sized molecules. Studies on the new MCO membrane have reported increased exchange of beta 2 microglobulin (11.8kDa), myoglobin (17kDa), kappa free light chains (22.5kDa) complement factor D (24kDa), alpha 1 microglobulin (33kDa), YKL-40 (40kDa) and lambda free light chains (45kDa) (http://www.hdxtheranova.com/clinicaldata.html). However, there are no data on the impact of these membranes on FGF-23 (32kDa)

This study will investigate the difference in clearance of FGF-23 between MCO membranes and conventional dialysis membranes. It will also analyse the pattern of production, intradialytic removal and re-accumulation of FGF-23.

5 Aims of the proposed research

Primary Objective:

1. Comparison of FGF 23 clearance between conventional and medium cut off membranes.

Secondary Objectives:

- 1. Assessment of intra-subject stability of FGF 23 clearance
- 2. Examine rate of FGF 23 re-accumulation rate
- 3. Examine impact of type of membrane, phosphate, calcium and urea clearance and PTH levels on FGF-23 clearance

6 Study Design

This will be a prospective randomised case-crossover design study. This design helps mitigate confounding variables as each patient acts as their own control.

Eligible participants will be stable haemodialysis patients on haemodialysis at Salford HD Unit and Bolton dialysis unit which is a satellite unit of Northern Care Alliance NHS Foundation Trust. Only patients who do not pass significant amount of urine (which indirectly indicates their own residual kidney function) and who have otherwise adequate dialysis treatment will be included (to allow comparison between different patients). Patients with active infection or cancer will not be included in the study as they are usually not in a steady state biochemical equilibrium to be able to assess impact of additional intervention.

Patients will be identified via electronic patient records (EPR) by the study coordinator and the research nurses from the Vascular Research Team (Research and Innovation Department, Northern Care Alliance NHS Foundation Trust). They will be approached by the research nurses and study coordinator during their routine vist for dialysis treatment and will be consented for entry into the study at their next routine appointment,. After informed consent, the patient will be randomly assigned to continue their dialysis treatments via either of the following two options via closed envelope.

Option 1: They will have one week of their usual thrice weekly dialysis treatment in a monitored fashion with traditional dialysis membrane. During this week, blood samples will be taken before and after dialysis via the dialysis circuits (without vene-puncture). Returned dialysate will also be collected and analyzed. Patients will then have three weeks of wash out period (when they will have their usual dialysis treatment). This will be followed by one week of monitored dialysis treatment with MCO dialysis membrane when again blood samples will be taken before and after dialysis and returned dialysate will be collected and analyzed.

Option 2: They will have one week of monitored dialysis treatment with MCO dialysis membrane. During this week, blood samples will be taken before and after dialysis via the dialysis circuits (without vene-puncture). Returned dialysate will also be collected and analyzed. This will be followed by three weeks of wash out period (when they will have their usual dialysis treatment). This will be followed by one week of monitored dialysis treatment with traditional dialysis membrane when again blood and dialysate samples will be taken.

Blood samples are routinely collected each month on dialysis without additional venepuncture. Monitored weeks will be timed to coincide with such collection thereby reducing excessive blood sampling. Returned dialysate is usually discarded and its sampling is not expected to cause extra discomfort to the patient.

Data will be anonymized and statistical analysis applied.

7 Detailed Plan of Investigation

7.1 Recruitment procedure

We aim to recruit 20 patients for our study. Eligible study participants receiving regular HD at Salford and Bolton HD units will be identified by the study coordinator and the research nurses from the Vascular Research Team (Research and Innovation Department, Northern Care Alliance NHS Foundation Trust) from the electronic patient records. Patients will be approached by a member of the research team during their routine visit for dialysis treatment and will be provided written and verbal information about the study in a clinic room to ensure the privacy. Participants will have sufficient time (at least 24 hours) to consider their involvement in the study and consent may be taken at their next routine appointment by the research nurses or the study coordinator following .response to any relevant questions in a clinic room to ensure the privacy.

7.2 Study protocol

7.2.1 Inclusion/Exclusion Criteria

7.2.1.a Inclusion Criteria:

• Patients aged 18 years and over with end stage renal failure on regular haemo-dialysis

7.2.1.b Exclusion Criteria:

- Lack of capacity to consent to treatment
- Significant residual urine output (> 500 ml of urine per 24 hours)
- Poor dialysis adequacy (URR<65%)
- < 18 years old

- Active infection
- Active malignancy

7.3 Study duration

Recruitment is expected to take about 6 weeks. After recruitment, the study itself will continue for five weeks in total; extendable to seven weeks in cases where wash out period needs to be extended due to acute illness. Last patient visit is expected to be after approximately 11 weeks. Processing of biological samples, statistical analysis and reporting of the results will be completed in 12 months.

7.4 Sample collection and handling

This study requires the collection of blood, which can easily be obtained, without additional venepuncture, directly from the dialysis machine before and after a monitored session. One 5ml lithium heparin blood tube and one 5ml serum blood tube, one EDTA and one 3.2% sodium citrate tube will be collected before and after monitored dialysis sessions. The serum will be left at room temperature for 15 minutes to clot before centrifugation to separate serum from clot. Serum will be pipetted into 1.5ml cryovials for storage at -80degC. The lithium heparin blood tube will be centrifuged to separate plasma from red cells. *The sodium citrate tubes will undergo two centrifuge spins, one at low speed and one high speed to remove remaining debris*.Plasma will be pipetted into 1.5ml cryovials for storage at -80degC.

7.5 Sample analysis

Routine biochemistry bone profile will be performed at the Salford Hospital biochemistry laboratory. Samples will also be transferred to the Department of Biochemistry, Research Institute Maastricht (CARIM), Maastricht University to be analysed for

FGF-23 levels and for selected relevant inflammatory calcification and coagulation factors.

7.6 Consent procedure

Potential participants meeting inclusion criteria will be approached by members of the research team at the Bolton haemodialysis satellite unit which is part of Northern Care Alliance NHS Foundation Trust or at Salford Dialysis Unit. All members of research team will have GCP training. In a private setting, potential participants will be asked from the research team about their willingness to be informed about this research study. Members of the research team will assess capacity of the patient. If the potential participant is deemed to have capacity, sufficient details regarding the study will be provided in order to gain informed consent. Information will be provided in form of verbal discussion and written leaflet. If patients require more time to make a decision they can take the information home and consent may be taken at their next routine appointment.

will be made to make information as accurate, balanced, and free of misleading information as possible. It will be ensured that potential participants are aware that the study is designed to assess impact of MCO dialyses membrane on blood levels of a molecule with potential harmful effects and no immediate clinical benefit is likely to emerge as a consequence. It will be explained that likely benefit will be a more clear understanding of clearance of this protein with MCO membranes which will help guide future research. Blood sample storage for potential future testing will be discussed and it will be explained that the data will be pseudoanonymised. In order to minimize risk of pressured decision, it will be clarified that their decision to participate in research study will have no bearing on their regular dialysis treatment or future interaction with dialysis/clinical staff. Alternative option of continuing with their usual dialysis will be emphasized to allow consent without any pressure.

7.7 Outcome measurement

FGF 23 clearance based on blood and dialysate testing for FGF 23 levels.

7.8 Withdrawal criteria

Participants will be allowed to withdraw from the study at any point. We will not collect any further data from this participant however will use data available during their time in the study for the final study analysis. If it is in the participant's best interest the clinician in charge of the study may also choose to withdraw the participant.

8 Regulatory and Ethical Considerations

8.1 Study conduct

- The study will be conducted in accordance with the UK Policy Framework for Health and Social Care Research and other applicable guidance.
- The study will not commence until all regulatory approvals are in place, which will include HRA Approval, REC Approval and confirmation from local R&D that the Trust has capacity and capability to carry out the research.

8.2 Monitoring and audit

- The study will be subject to the standard procedures for monitoring and auditing of studies by the sponsor.
- Any changes to the protocol will be agreed with the sponsor prior to submission to NHS research ethics committee for review with the exception of where urgent safety measures apply.
- All staff working in the study will have completed appropriate training to undertake the duties delegated to them by the Principal investigator such an ICH-GCP.

8.3 Protocol deviations

- Any deviations to the protocol will be reported to the sponsor within 24 hours of the occurrence to allow an impact assessment to be completed.
- Consideration will be given to the nature of the deviation, its causes and the potential impact on the study.
- Where necessary, a deviation from the protocol may lead to an amendment to the protocol

8.4 Study progress reports

The PI and research team will submit progress reports to the Sponsor as requested and prior to submission to NHS REC, in accordance with the terms and condition of the study approval.

8.5 Stopping rules

It is not anticipated that the study will be stopped prior to its intended end-date. However, the study will be halted if:

- New information comes to light which means that the aims of the study are futile.
- Safety issues come to light regarding the intervention.
- Resources to conduct the study are no longer available.

9 Record keeping and data management

- All outcome measures will be recorded on standardised data collection forms. These, together with the exclusion criteria screening proformas and consent forms, will all be stored in a secure area at the Vascular Research Team, Research and Innovation Department at Northern Care Alliance NHS Foundation Trust.
- Given this is a prospective data collection, the data will be pseudo anonymised before being stored. A separate database with matched patient study code numbers will contain patient names, date of birth, hospital numbers and contact details. The data will be stored on the NHS computer with following layers of security.
 - Patient data will only be saved on NHS computers.
 - NHS Computer will be located in secure NHS facility (swipe card/code protected entrance to the room) where only health care professionals are allowed to access.
 - \circ $\,$ Computers will be protected by start-up password.
 - Files will be password protected.
 - The PI, research nurses and study coordinators will have access to the data.
- Under the General Data Protection Regulation (GDPR), data will be anonymized, encrypted where necessary and access will be strictly restricted. Use of laptops and other portable devices will be avoided. Where it is necessary for them to be used, data will be encrypted and the data uploaded onto a secure server or desktop as soon as possible and the data removed from the portable device as soon as possible and using appropriate data destruction software. Under no circumstances, patients' or research participants" personal data will be stored on a home or other personal computer.

10 Statistical analyses and data handling

Statistical support has been provided by [name], Biostats Research Assistant (Research Assistant at University of Manchester.

The clearance of FGF 23 will be calculated as $(FGF23_{pre} - FGF 23_{post})/FGF 23_{pre}$ for each dialysis session and intra-subject stability will be assessed with repeated measures ANOVA or Friedman test, depending on the distribution of the data.

The re-accumulation rate of FGF 23 will be measured as (FGF23_{pre} – FGF 23 $_{post}$ previous HD session)/FGF-23_{post} previous HD session.

The average FGF 23 clearance values on conventional membranes will be compared with average values on medium cut-off membranes with paired-t test or Wilcoxon signed-rank test depending on the distribution of the data (irrespective of whether intra-subject stability is confirmed or not)

Further analysis will depend on the results of the intra-subject stability of FGF 23 clearance, that is, either it may be appropriate that the first HD session of each monitored session will be used for the analysis or each dialysis may need to be treated as separate event. In this case calcium, phosphate, URR, PTH, type of membrane and FGF -23 will be entered in a multiple linear regression analysis to determine relationships with FGF 23 clearance.

The data collected will be stored pseudo anonymised. A separate database with matched patient study code numbers will contain patient names, date of birth, hospital numbers and contact details. The data will be stored on the laptop computer and will be password protected with restricted access.

Power Calculation;

Sample size was calculated calculation was based on the recent study by Damasiewicz et al (6). If the log difference is 7.47 or greater, with 20 patients the study has a 80 % chance of detecting it at a two-sided 0.05 significance level.

11 Dissemination of Results and Publication Policy

Results will be presented in local/regional meetings and published in a journal. Results of the study will be publicised more widely via the Citizen Scientist initiative (see http://www.citizenscientist.org.uk/).

12 References

1. Suassuna PGA, de Paula RB, Sanders-Pinheiro H, Moe OW, Hu MC. Fibroblast growth factor 21 in chronic kidney disease. J Nephrol. 2018 Nov 14.

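### The clearance formula takes the post-dialysis FGF-23 level uncorrected for fluid removal, so removal within each membrane arm is understated and can read as zero or negative when true removal is small

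*Protocol*

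**What the plan says.** Protocol section 10 defines the outcome variable: "The clearance of FGF 23 will be calculated as $(FGF23_{pre} - FGF 23_{post})/FGF 23_{pre}$ for each dialysis session". Averages of this quantity are then compared between membranes: "The average FGF 23 clearance values on conventional membranes will be compared with average values on medium cut-off membranes with paired-t test", with the Wilcoxon signed-rank test as the alternative. This serves the primary objective in section 5.

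The same raw post-dialysis level is both reference and divisor for re-accumulation. Section 10 introduces that formula with "The re-accumulation rate of FGF 23 will be measured as" and ends it with "previous HD session)/FGF-23_{post} previous HD session".

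The regression in section 10 has no term for fluid: "In this case calcium, phosphate, URR, PTH, type of membrane and FGF -23 will be entered in a multiple linear regression analysis". The protocol nowhere mentions ultrafiltration, body weight, haematocrit or protein, whether in the formulas, the sampling plan (section 7.4) or the covariates.

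Section 7.7 describes the outcome more broadly: "FGF 23 clearance based on blood and dialysate testing for FGF 23 levels". Section 6 has dialysate collected in both monitored weeks. No formula in section 10 uses it.

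**The concern.** Section 7.2.1.b excludes patients with "Significant residual urine output (> 500 ml of urine per 24 hours", so those enrolled pass little urine and net fluid removal can be expected at most sessions. That is an inference; the protocol does not state it. Fluid removal shrinks the volume in which the retained FGF-23 is dissolved, so the post-dialysis level goes up for a reason unrelated to the membrane.

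Three results are exposed.

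- **Absolute removal.** The protocol's opening summary asks whether the new membrane can remove FGF-23 and makes further studies depend on the answer. Section 4 notes the gap: "However, there are no data on the impact of these membranes on FGF-23 (32kDa". A membrane with modest true removal could be reported as having none.
- **Intra-subject stability.** Section 10 lets the form of the later analysis depend on this result. Sessions that differ only in fluid removed would look unstable.
- **Re-accumulation.** Dilution by fluid regained between sessions is mixed with new FGF-23.

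**Working it through.** The documents give no figure for this effect, so there is none to reproduce. The check is a mass balance.

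**Inputs.** From the protocol: the two formulas, thrice-weekly sessions (section 6) and the paired analysis (section 10). Assumed: a single pool equal to 20% of post-dialysis weight, all removed fluid coming from that pool, 70 kg post-dialysis weight, 2.5 L removed, and an SD of 0.7 L in fluid removed. True removal R means the net fractional fall in the amount of FGF-23 in the pool.

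**Step 1: concentration factor.** k = V_pre / V_post = 1 + fluid removed / (0.2 × post-dialysis weight).

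- 70 kg, 2.5 L: 1 + 2.5/14 = 1.179
- 80 kg, 1 L: 1 + 1/16 = 1.06
- 60 kg, 3 L: 1 + 3/12 = 1.25

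**Step 2: what the formula reads.** Raw ratio = 1 - k(1 - R). The error is -(k - 1)(1 - R), which is below zero whenever k > 1 and R < 1. The raw ratio is negative when R < 1 - 1/k.

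| True removal R | k = 1.06 | k = 1.179 | k = 1.25 |
|---|---|---|---|
| 10% | +4.6% | -6.1% | -12.5% |
| 20% | +15.2% | +5.7% | 0.0% |
| 30% | +25.8% | +17.5% | +12.5% |

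At k = 1.179 the raw ratio is negative for any true removal below 1 - 1/1.179 = 15%.

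**Step 3: volume fraction.** With 70 kg and 2.5 L, a fraction of 15% gives k = 1 + 2.5/10.5 = 1.238, and 25% gives 1 + 2.5/17.5 = 1.143. A true 10% then reads as -11.4% or -2.9%.

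**Step 4: membrane difference.** With the same k in both weeks, raw difference = k(R_MCO - R_conventional). A true 20-point difference reads as 0.20 × 1.179 = 0.236. It is enlarged, keeps its sign, and stays at zero if the true difference is zero.

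**Step 5: noise.** For one session at R = 10%: 0.9 × 0.7/14 = 0.045. Over three independent sessions: 0.045/√3 = 0.026. For the difference between two such averages: 0.026 × √2 = 0.037. These combine in quadrature: an assumed base SD of 0.10 for a patient's weekly average becomes √(0.10² + 0.026²) = 0.103.

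**Step 6: apparent instability.** At 14 L and R = 10%, a 2 L session reads 1 - 0.9 × 1.143 = -2.9% and a 3 L session reads 1 - 0.9 × 1.214 = -9.3%. True removal is identical, yet the readings differ by 6.4 points. A thrice-weekly schedule has one longer gap each week, so such a pattern could recur.

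**Step 7: re-accumulation.** With no new FGF-23 and all the fluid regained, the next pre-dialysis level is the previous post level divided by k. The formula reads 1/k - 1 = 1/1.179 - 1 = -15%.

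**The case against.** The strongest reply is that the primary objective is a comparison, made within patients in a randomised crossover. If fluid removal is similar in the two weeks, each patient's difference is multiplied by that patient's own k, the spread is scaled with it, and the test result hardly changes. This stands. A reader might infer that the membrane contrast is understated or biased. The documents do not support that: the contrast is scaled up, order is randomised, and nothing in the protocol suggests that fluid removal differs by membrane. A spurious contrast needs unequal removal. For example, k of 1.1 against 1.2 with 10% true removal in both weeks gives 0.9 × 0.1 = 9 points.

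A second reply is that dialysate is collected and analysed for FGF-23, and finding it there is direct evidence of removal whatever happens to plasma volume. This also stands, so it goes too far to infer that the trial could miss removal altogether. But section 10 defines clearance from blood alone, so the reported clearance is not protected.

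Third, the noise is small once sessions are averaged. That is right for the primary comparison. It does not help the session-by-session stability analysis.

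Fourth, the size depends wholly on inputs the protocol does not give. That is true of the magnitude. The direction follows from the algebra whenever net fluid is removed from the pool.

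**Conclusion.** The point holds for absolute removal within each membrane arm. The formula understates it, and small true removal can read as zero or negative. Under the stated assumptions the factor is about 1.18 (1.06 to 1.25), and 10% true removal reads as about -6% (+5% to -12.5%). Re-accumulation and intra-subject stability are affected too. The paired membrane test is largely intact if fluid removal is similar in both weeks, with modest added noise of about 0.026 per three-session average (SD 0.7 L, 10% true removal, independent sessions). Because the protocol fixes the formula itself, this is not a detail left open for an analysis plan. It should be corrected, but it does not invalidate the primary comparison.

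**What to change.** - Record weight before and after every monitored session on the data collection form.
- Define clearance as (FGF23_pre - FGF23_post,corr)/FGF23_pre, with FGF23_post,corr = FGF23_post / [1 + (weight_pre - weight_post)/(0.2 × weight_post)]. Use it for the membrane comparison, the stability analysis and the regression.
- For re-accumulation, correct for dilution with the interdialytic gain, not with the previous session's weight loss; the two can differ when gaps between sessions are unequal. With g = 1 + (next pre-session weight - previous post-session weight)/(0.2 × previous post-session weight), use (g × FGF23_pre - FGF23_post,previous)/FGF23_post,previous.
- Report the uncorrected ratio, and volume fractions of 15% to 25%, as sensitivity analyses.

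The cost is two weights per monitored session (assumed to be taken already) and two lines of formula. There is no extra blood sample and no change to treatment, schedule or sample size. The downside is reliance on an assumed volume fraction, which the sensitivity analyses expose. The weights should be specified before data collection, since unrecorded ones may be hard to recover.

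### Intra-subject stability of FGF-23 clearance is judged by tests of session means or ranks, which do not measure within-patient variability, and that result steers the later regression

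*Protocol*

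**What the plan says.** Section 5 lists as the first secondary objective: "Assessment of intra-subject stability of FGF 23 clearance". Section 10 defines clearance for each dialysis session as the proportional fall in FGF-23 from before to after dialysis, and gives one method for the objective: "intra-subject stability will be assessed with repeated measures ANOVA or Friedman test, depending on the distribution of the data". It names no within-patient SD, coefficient of variation, intraclass correlation or stability margin.

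Section 10 then says: "Further analysis will depend on the results of the intra-subject stability of FGF 23 clearance". It offers two routes. One is tentative: "either it may be appropriate that the first HD session of each monitored session will be used for the analysis". The other is that "each dialysis may need to be treated as separate event". A multiple linear regression of clearance on membrane type and biochemistry follows, which serves secondary objective 3.

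The membrane comparison under the primary objective stands apart. It uses each patient's average clearance per membrane and is made "irrespective of whether intra-subject stability is confirmed or not".

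**The concern.** Intra-subject stability is a question about dispersion: how far one patient's clearance moves from session to session. The two named tests address location: whether the group's mean or rank moves systematically between sessions. In repeated measures ANOVA the within-patient scatter is the error term, so it sits in the denominator of F. Patients whose clearance swings widely, but in no common direction, will usually give a non-significant result. Patients who are highly reproducible but share a small common shift can give a significant one.

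Two things are at stake. Secondary objective 1 could be reported as met or not met on a statistic that does not measure it. The same result would also help to choose which sessions enter the regression for secondary objective 3, so the analysis set would be picked after seeing the data, by a test that carries little information about the property in question.

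**Working it through.** **Inputs from the protocol.** Section 7.1: "We aim to recruit 20 patients for our study". Section 6: dialysis is three times weekly, with one monitored week per membrane. Section 10: the tests and the two routes. The protocol gives no variance for clearance, so every SD, shift and ICC below is an assumption on the scale of the reduction ratio. It also states no power or precision for the stability question, so there is no figure to reproduce.

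**1. Equal session means.** When no session differs systematically, each test rejects at its nominal 5%, whatever the within-patient SD. A simulation (20,000 runs, 20 patients, 3 sessions, assumed between-patient SD 0.10) confirms this:

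| Within-patient SD | ICC | ANOVA rejects | Friedman rejects |
|---|---|---|---|
| 0.01 | 0.99 | 4.6% | 5.0% |
| 0.10 | 0.50 | 5.0% | 5.1% |
| 0.40 | 0.06 | 5.1% | 5.4% |

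Here ICC = between-patient variance / (between-patient + within-patient variance); for example 0.10² / (0.10² + 0.40²) = 0.0100 / 0.1700 = 0.06. Near-perfect and very poor reproducibility give the same answer.

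**2. A real shift of 0.05 in one of three sessions.** The deviations from the grand mean are 0.05 × (2/3, −1/3, −1/3), with sum of squares 0.0025 × 6/9 = 0.001667. The non-centrality is λ = 20 × 0.001667 / SD² = 0.03333 / SD². The F test has 2 and 38 degrees of freedom and a critical value of 3.245.

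| Within-patient SD | λ | Power |
|---|---|---|
| 0.05 | 13.33 | 0.891 |
| 0.10 | 3.33 | 0.329 |
| 0.15 | 1.48 | 0.166 |
| 0.20 | 0.83 | 0.113 |

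The same drift is usually detected when patients are consistent and usually missed when they are not.

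**3. The converse.** In the same simulation, a shift of 0.01 in sessions 2 and 3 with within-patient SD 0.01 (ICC 0.99) was significant in 89% of runs by ANOVA and 77% by Friedman. A larger shift of 0.03 with within-patient SD 0.40 (ICC 0.06) was significant in 5.5% and 5.4%. The reproducible patients are the ones flagged.

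**4. What the switch governs.** Planned sessions: 20 patients × 2 weeks × 3 = 120. First session of each week only: 20 × 2 × 1 = 40, so 80 of 120 (66.7%) would not enter the further regression. The other route uses all 120 but states no patient term, although six sessions come from each patient. As an illustration, for a covariate that is constant within a patient and an assumed ICC of 0.5, the variance is understated by a factor of 1 + 5 × 0.5 = 3.5. A nominal 5% test then has a true error rate of about 2 × P(Z > 1.96/√3.5) = 2 × P(Z > 1.048) ≈ 29%.

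**The case against.** The strongest defence is that stability may mean only the absence of systematic drift across the week's sessions. The protocol does not define the term, and for that narrower question ANOVA or Friedman is coherent. That is a good reason to keep the session test. It does not rescue the plan, because the objective is worded as intra-subject and a group-level test cannot describe the individual. A non-significant result in 20 patients does not show the absence of drift either.

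It can also be said that the ANOVA residual mean square yields a within-patient SD, and that a separate analysis plan may report it. That is true for ANOVA, but the protocol does not say it will be used, and Friedman, the named alternative, supplies no such estimate.

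The decision rule is only partly written. Section 10 gives no significance threshold, does not say which result leads to which route, and words the first-session option as a possibility. It may also tie the regression to the separate-event route alone. Equating non-significance with stability is therefore an inference. It is a reasonable one, since section 10 speaks of stability being confirmed or not and names no other criterion.

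Three stronger readings are not supported:
- A reader might infer that two thirds of the sessions could be lost from the primary comparison. Section 10 expressly exempts that comparison. Any loss of precision from using one session instead of three concerns, at most, a membrane term in the further regression.
- A reader might infer that the tests call clearance stable precisely when it is unstable. With equal session means the result does not depend on within-patient variability at all; the inverse relation appears only when there is a real shift.
- A reader might infer that the first session is unrepresentative because it follows the long interdialytic gap. The protocol does not say on which weekday monitoring starts.

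**Conclusion.** The point holds for secondary objective 1 and for the further regression under secondary objective 3; no effect on the primary comparison is shown. As written, the only method for intra-subject stability is insensitive to within-patient variability when session means are equal (about 95% non-significant at any SD). When means differ, it becomes less likely to signal instability as variability grows (power 0.89, 0.33, 0.17 and 0.11 at within-patient SDs of 0.05, 0.10, 0.15 and 0.20). Those power values rest on an assumed 0.05 shift in one session, assumed SDs and 20 patients with complete data. The direction does not rest on them, because it follows from the form of the F statistic.

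Letting this result choose between 40 and 120 sessions for the regression has no sound basis, even though the first-session option is only tentative. The change should be made; it is not critical to the main result.

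**What to change.** In section 10, or in the analysis plan if there is one:

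1. Assess secondary objective 1 by estimation: within-patient SD (or CV) and ICC of clearance, separately for each membrane, with 95% confidence intervals. Working per membrane also settles a point left open, since a test pooled over all six sessions would read a membrane effect as instability.
2. Keep the repeated measures ANOVA or Friedman test as a descriptive check for systematic drift between sessions, and do not treat a non-significant result as confirmation of stability.
3. Delete the sentence that makes further analysis depend on the stability result.
4. Fit the further regression to all sessions in a mixed model with a random patient effect.
5. Leave the exemption of the primary membrane comparison as it is.

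The cost is a change of wording and slightly more analysis work. The sessions are already planned, so no extra samples or patients are needed.
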